3.3.2 Patient population selection criteria

All patients with NSCLC attending participating hospitals during the pre-specified period will be eligible to participate in the study.

Patients will be asked to sign an informed consent form which specifies that there will be no change in clinical management because of the study and that it only involves collecting information[†]

All patients regardless of whether they are participating in clinical trials or not are eligible to be included in the study. This is a purely observational study, therefore participation in this study will not interfere with participation in a clinical trial. The participation in this study will not prevent the patient from being given the opportunity of receiving an investigational product or participating in another study.

A sample of patients (25% of the whole sample) will be asked to complete Quality of Life questionnaires when attending the programmed assessment visits to the physician. Only patients who are not participating in clinical trials will be asked to participate in the Quality of Life sub-study. These patients will be asked to sign a specific informed consent form.

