2.1.2 Analytical objectives

- To assess the differences in patient characteristics, disease stage (differentiating between non-advanced disease, locally advanced disease, metastatic disease), and in clinical management across Central Eastern European countries and Russia.
- To detect differences in clinical outcomes and related factors among countries.
- To identify factors associated with clinical outcomes (patient, disease stage –see above- and clinical management related factors): predictive modelling for improved patient outcome.

Version No: 4.0 Date: 8 December 2009

- To identify factors associated with the different levels of functional status and quality of life.

- To compare the use of health care resources among countries.

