3.3.2.1 Inclusion Criteria

For inclusion in the study, patients must meet all of the following criteria:

- 1. Confirmed NSCLC diagnosis (e.g. bronchoscopic biopsy or FNAB), all stages, men and women, attending the responsible department of treating this type of patients for the first time between January 1st, 2010 and August 1st, 2010.
- 2. For PRO sub-sample: ability to read and write since they will be asked to participate in the PRO part of the study. Selection will not be based on the disease stage of each patient, in order to avoid a selection bias.
- 3. 18 years of age or more.

-

[†] Only when required by local authorities.

Version No: 4.0

Date: 8 December 2009

3.3.2.2 **Exclusion Criteria**

According to the study design there will not be any exclusion criteria in order to provide a high external validity and to obtain the most accurate real daily practice information.

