4.2 Screening and demographic measurements

Each site will be responsible for maintaining an updated record of the number of patients who are included or not included in this study. An explanation of why patients were not included must be available.

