8.3 Informed consent

The information given below refers to any ICF necessary for the performance of this study.

It should be taken into account that some local authorities do no require informed consent for obtaining disease-related data related from medical records which are covered by data protection regulations and the approval of an ethics committee.

Thus a signed ICF from the study population will only be required when the local authorities specifically require it. The procedure for general patients and the PRO sample is described below.

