8.3.1 Informed Consent requesting procedures

Informed consent must be given by all patients willing to participate in the study, if required in local regulations.

Version No: 4.0 Date: 8 December 2009

The principal investigator(s) at each centre will ensure that the patient participating in the study is given full and adequate oral and written information about the nature, purpose, possible risk and benefit of the study. Patients must also be notified that they are free to withdraw from the study at any time. The patient should be given the opportunity to ask questions and allowed time to consider the information provided.

The patient's signed and dated informed consent must be obtained before conducting any activities related with the study.

The principal investigator(s) must keep the original, signed Informed Consent Form. A copy of the signed Informed Consent Form must be given to the patient.

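### Signed consent is an entry condition only where local authorities require it, so between-country comparisons may partly reflect the consent rule if both kinds of country take part

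*Protocol*

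**What the plan says.** Section 3.3.2 of the protocol says: "Patients will be asked to sign an informed consent form which specifies that there will be no change in clinical management". A dagger footnote, printed under section 3.3.2.1, restricts the sentence: "Only when required by local authorities". Section 8.3 repeats the restriction: "Thus a signed ICF from the study population will only be required when the local authorities specifically require it". Section 8.3.1 makes consent a condition of taking part where it applies ("Informed consent must be given by all patients willing to participate in the study, if required in local regulations") and fixes its timing: "The patient's signed and dated informed consent must be obtained before conducting any activities related with the study".

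The data source is the medical record (section 3.1). The same section lets patients be included retrospectively when ethics approval comes late, provided that their first attendance fell in the enrolment period.

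Three of the five analytical objectives in section 2.1.2 compare countries: the first (characteristics, stage and management), the second ("To detect differences in clinical outcomes and related factors among countries") and the fifth (use of resources). Section 3.2 treats the avoidance of selection bias, and the inclusion of every attending patient, as essential.

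Three provisions bear on who is missed:
- Section 3.3.1 tells each investigator to invite every first attender who meets the criteria.
- Section 4.2 sets up a site log: "Each site will be responsible for maintaining an updated record of the number of patients who are included or not included in this study". The reason for each non-inclusion must also be available.
- Section 7.1 treats a high rejection rate at a site, or fewer identified NSCLC patients than expected, as a signal to evaluate and correct.

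**The concern.** The rule that forms the cohort can differ from one country to the next. With a consent requirement, a patient must be alive, able and willing to sign before anything is recorded. Without one, any first attender can be entered from the record. Retrospective inclusion can widen the gap: a patient who has already died can be entered where no form is needed, but not where one is.

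Patients lost before signature may well have a worse prognosis and less treatment than the rest. If so, consent countries would show better survival and more active treatment with no difference in care. Local authorities set the rule, so it is largely constant within a country, and a country term in a model cannot separate it from a true country effect.

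The point concerns who enters the main cohort, not who withdraws later. The quality-of-life sub-study has its own consent form under section 3.3.2 and is a separate matter.

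**Working it through.** The protocol gives no figure for refusal, delay to consent or prognosis of patients not entered, so there is no stated figure on this point to reproduce. What follows is an illustration for stage IIIB/IV patients only.

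**Inputs from the protocol**
- One-year survival of 35%, so mortality of 65%, and median survival of 7 to 10 months. Both are for stage IIIB/IV on first-line chemotherapy (section 1.1).
- 500 patients planned in Russia (summary). No other country's number is given.
- Precision of 0.04 for a proportion of 0.5 with 600 patients (section 6.4), used here only as a yardstick. It reproduces: (1.96/0.04)² × 0.25 ≈ 600.

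**Assumptions, not in the protocol**
- Share not entered, x: 10% or 20%.
- One-year mortality of those not entered, m: 70% or 90%.
- True mortality is the same in both countries.

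**Selection at entry.** Mortality among those entered is (0.65 − m·x)/(1 − x).
- x = 0.10, m = 0.70: 0.58/0.90 = 64.4%, understated by 0.6 points.
- x = 0.10, m = 0.90: 0.56/0.90 = 62.2%, understated by 2.8 points.
- x = 0.20, m = 0.70: 0.51/0.80 = 63.75%, understated by about 1.3 points.
- x = 0.20, m = 0.90: 0.47/0.80 = 58.75%, understated by about 6.3 points.

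The shift equals x(m − 0.65)/(1 − x). It is zero when m = 0.65, that is, when loss is unrelated to prognosis.

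**Against sampling error.** For two countries of 500 patients each (500 is stated for Russia only), the standard error of the difference is √(2 × 0.65 × 0.35/500) = 3.0 points, and 1.96 standard errors are 5.9 points. Both 10% cases lie below one standard error. Only the most adverse case, 20% not entered with 90% mortality, exceeds 5.9 points, and it alone exceeds the 4-point yardstick. Unlike sampling error, the shift does not shrink with more patients.

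**Early death alone.** Take exponential survival with a median of 7 or 10 months and assume one month from first attendance to signature.
- Median 7 months: 1 − 2^(−1/7) = 9.4% die before signing. Twelve-month survival from first attendance is 30.5% in all patients and 33.6% in those who live to sign.
- Median 10 months: 1 − 2^(−1/10) = 6.7% die before signing. The two survival figures are 43.5% and 46.7%.

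That is a shift of about 3 points. Applying a chemotherapy median from first attendance is itself an assumption.

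**The case against.** The strongest reply has four parts.

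- **The bias is conditional.** No section says which countries require a form or that both kinds take part. Section 8.3 says only that some authorities do not ask for one. A reader might infer that consent countries will show lower mortality and more treatment. The documents do not support that: they give no refusal rate, delay or prognosis for patients not entered. This stands, and it limits the point to a possible bias.
- **There are safeguards.** A reader might take the section 4.2 log to be the only one, but sections 3.3.1 and 7.1 add the instruction to invite everyone and the two monitoring signals. This also stands. However, the log requires only numbers and reasons, the signals are aimed at investigators' compliance, and the protocol links none of them to the country comparison.
- **Analysis belongs in the SAP.** Section 6.1 promises one, and section 6.3 lists stage, histology and performance status as model variables, which would absorb part of a prognostic difference. This stands for the choice of analysis. It does not stand for data: an analysis plan cannot use a consent rule, consent date or participation count that was never collected. Nor does adjustment for stage remove selection within a stage.
- **The consent rule is a matter of law.** True, and nothing here asks to change it. Since section 8.3.1 puts consent before any study activity, central patient-level data on people who refused would be contestable. The fix therefore relies on aggregate counts.

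Section 8.3.1's timing sentence might also be read as contradicting section 8.3. It does not: section 8.3 introduces its content as applying to whichever forms are needed, and section 8.3.1 opens with the same condition.

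**Conclusion.** The point holds in a conditional form. If both consent rules occur among the participating countries, the cohorts are formed differently, and the three between-country objectives may partly measure that difference, against the standard that section 3.2 sets. Better apparent outcomes in consent countries are the likely direction, by inference only.

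The size cannot be derived from the documents. The illustrative range of 0.6 to 6.3 points rests on assumed values for both the share and the mortality of patients not entered. It should not be carried over to the whole cohort, which takes all stages and includes untreated patients. No size is offered for treatment or resource use. This is a worthwhile, cheap improvement, not a demonstrated bias.

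**What to change.** 1. Record for each site whether a signed form was required for the main cohort. Record for each patient the dates of first attendance and of consent or inclusion. Section 4.1.2 already collects visit dates.
2. From the existing section 4.2 log, report by country the aggregate counts of first attenders, of those included, and of those not included by reason (refused; died or too ill before signing; other). Add anonymous stage group only where local law permits.
3. For between-country survival and treatment comparisons, add a sensitivity analysis that uses first attendance as the common time origin, with late entry at consent, or one common landmark in all countries. Show contrasts within the same consent rule where more than one country shares it.
4. State that the late-entry or landmark analysis deals with early death only. Refusers, and patients too ill to sign who survive the landmark, remain missing in consent countries. The participation counts and the within-rule contrasts are what bear on that.

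Cost: a few data fields, a short summary of a log that sites already keep, and a little more analysis. Some precision is lost, and early deaths do not count in the landmark analysis.

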3.3.2.1 Inclusion Criteria

For inclusion in the study, patients must meet all of the following criteria:

- 1. Confirmed NSCLC diagnosis (e.g. bronchoscopic biopsy or FNAB), all stages, men and women, attending the responsible department of treating this type of patients for the first time between January 1st, 2010 and August 1st, 2010.
- 2. For PRO sub-sample: ability to read and write since they will be asked to participate in the PRO part of the study. Selection will not be based on the disease stage of each patient, in order to avoid a selection bias.
- 3. 18 years of age or more.

-

[†] Only when required by local authorities.

Version No: 4.0

Date: 8 December 2009

3.3.2.2 **Exclusion Criteria**

According to the study design there will not be any exclusion criteria in order to provide a high external validity and to obtain the most accurate real daily practice information.

3.3.3 Discontinuation of patients from assessment

3.3.3.1 Criteria for Discontinuation

The following criteria for withdrawal only apply to patients who, according to local regulations, need to sign the ICF in order to participate in this study. Thus these criteria apply to all patients included in the PRO sample, and to all patients when the ICF is required for all participating subjects:

- 1. Voluntary withdrawal by the patient who is free to withdraw from this NIS at any time, without prejudice to further treatment.
- 2. Severe non-compliance with questionnaire instructions as judged by the investigator and/or AstraZeneca's local coordinator.
- 3. required Inadequate enrolment e.g., the patient does not meet the inclusion/exclusion criteria for the study.

3.3.3.2 **Procedures for discontinuation**

Patients who wish to withdraw from the PRO sub-study will be immediately withdrawn but the information from the medical record will continue to be collected $^{\bar{I}}$.

4. MEASUREMENTS OF STUDY VARIABLES AND **DEFINITIONS OF OUTCOME VARIABLES**

4.1 **Study Variables**

4.1.1 Information regarding the patients and their disease

Patient Demographics and any other general patient information: Some of the study variables are considered as risk factors of disease progression and functional status therefore, in order to describe the study population, the following information will be collected:

- Gender.
- Date of birth.
- Ethnicity.
- Smoking habits.

[‡] When ICF is not required for medical record data collection

Protocol of Non-Interventional Study

Drug Substance: N/A

NIS Code: NIS-ORU-IRE-2009/1

Version No: 4.0 Date: 8 December 2009

Co-morbidities

Disease information: All aspects related with the disease.

- Disease stage and TNM classification. Only at first visit.
- Primary tumour location: Only at first visit.
- Histological classification and degree of differentiation. (Only at first visit).
- Extent of the disease.
- Related symptoms.
- Molecular biomarkers. (When available). Just to have information on whether such analyses were performed or not in real clinical practice.

Patient Evolution: All information on how the patient is progressing as regards the disease and on therapy-related factors.

- Performance Status (PS)/ECOG, including at diagnosis.
- Weight loss.
- Progression of disease. To be taken into account if disease progression is based on RECIST criteria and/or any other clinical assessment.
- Treatment response: Non-response, partial response, stable disease and complete response according to RECIST evaluation and/or any other clinical assessment.
- Death: Disease-related or for other reasons.
- Disease-related events: Any event the patient experiences that is related with the NSCLC condition (e.g. hospitalisation, primary care consultation, etc).
- Therapy-related events: Any event related to receiving NSCLC treatment (e.g. adverse events).

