1. INTRODUCTION

1.1 Background and rationale

Lung cancer is one of the leading causes of death worldwide. Of the 7.3 million deaths caused by cancer every year, 17% are due to Lung Cancer. Prevalence of this disease during 2006 alone in Europe was 386,300 total cases, and 334,800 died during the same period¹.

Of the entire lung cancer population, Non-Small Cell Lung Cancer (NSCLC) is the most common (around 80%) compared with Small Cell Lung Cancer (SCLC)². Squamous Cell Lung Cancer and Adenocarcinoma are the most common subtypes in Europe between 46.5%³-33%⁴ and 23.6%³-30%⁴ respectively.

Histopathologically confirmed lung cancer is essential for optimal management of the individual patient and must be secured before chemotherapy and radiotherapy are initiated. However, in rare cases it may be impossible to obtain tumour tissue for examination due to multiple significant co-morbidities or poor performance status. Furthermore, resources available for obtaining correct diagnosis and TNM classification are likely to differ among centres, exemplified by the lack of resources for PET examination in many sites throughout Central Eastern Europe and Russia.

According to national and international guidelines, surgery, chemotherapy and radiotherapy are the cornerstones of NSCLC treatment. Individualized supportive care should constitute an essential element in the management of all patients with NSCLC. Treatment choices are determined by the stage of the disease at each moment and the patient's individual condition (performance status, co-morbidity and age).

The median survival for patients with stage IIIB or IV disease with current first-line chemotherapy regimens is approximately 7-10 months, the one-year survival rate is 35% and response rates range between 17-37%. Once patients experience treatment failure with initial therapy, response to further systemic treatment is approximately 10% Further progress is anticipated with the novel therapeutic approach of combining existing chemotherapy with drugs that target specific signalling pathways of lung cancer progression.

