The eCRF will be completed at each evaluation visit, entering information on this visit and any other relevant data related to any intermediate visits between the last evaluation visit and the current visit. The study termination module of the eCRF must be completed at the time the investigator is aware of patient's death or withdrawal.

Figure 1 Study flow chart

[figure not shown]

Table 1 Study plan

Time	Inclusion assessment	Each evaluation visit
Informed Consent (when necessary)	X	
Patient Demographics	X	
Site information*	X	
Smoking habits	X	
Disease Information	X	X
Diagnosis information	X	
Therapy information	X	X
Clinical outcomes		X
Events due to therapy and/or disease		X
Adverse events due to therapy		X
Use of resources	X	X
Patient Reported Outcomes (a sample of patients)	X	X

Version No: 4.0 Date: 8 December 2009

Time	Inclusion assessment	Each evaluation visit
Study termination (when investigator is aware)		X

^{*}At the time of registering a participating site

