6.2 Analysis of outcome variables in relation to objectives and hypotheses

Three groups will be created from baseline evaluation for the purpose of data analysis. The patients will be divided according to the baseline stage of their disease (non-advanced NSCLC patients, locally advanced NSCLC patients and metastatic NSCLC patients). For each of them the following variables will be considered:

- Clinical evolution from baseline to each visit:
 - o Changes in number of disease-related symptoms.
 - o Changes in the extent of the disease.
- Treatment response from baseline to each visit:
 - o Number of patients with complete response to treatment.
 - Number of patients with partial response to treatment.
 - Number of patients with stable disease under treatment.
 - o Number of patients with progression of disease after treatment.
 - O Progression-free time from the last progression or diagnosis to new progression of disease during the study period. The main analysis of the time to disease progression will be a Cox proportional hazards model to estimate the hazard ratio of progression among the analysis groups, with 95% confidence intervals. This will be a 2-sided test of the hypothesis, with a statistical significance level of 0.05. The assigned treatment will be included as a covariate.
- Treatment-related events.

Protocol of Non-Interventional Study

Drug Substance: N/A

NIS Code: NIS-ORU-IRE-2009/1

Version No: 4.0 Date: 8 December 2009

> o Mean number of patients with any treatment related event during the study period.

> o Mean number of patients with any serious treatment related event during the study period.

Mortality.

- o Number of patients with documented death during the study period.
- o Number of patients with a documented death due to NSCLC during the study period.

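### Stage and TNM are recorded only at the first visit although entry does not require completed staging, so patients with an open work-up can be placed in the wrong baseline-stage group

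*Protocol*

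**What the plan says.** - **When stage is recorded.** Protocol Section 4.1.1: "Disease stage and TNM classification. Only at first visit". Primary tumour location and histology carry the same limit. "Extent of the disease" is in the same list without it, and Table 1 in Section 3.1 ticks disease information both at inclusion and at each evaluation visit.
- **Entry.** Section 3.3.2.1 asks for "Confirmed NSCLC diagnosis (e.g. bronchoscopic biopsy or FNAB), all stages", together with first attendance at the treating department in the enrolment window and adult age. Completed staging is not a condition.
- **How stage is used.** Section 6.2: "The patients will be divided according to the baseline stage of their disease", giving a non-advanced, a locally advanced and a metastatic group. The Cox model for progression compares these groups. Section 6.3 uses stage as a factor in the logistic and general linear models. Section 2.1.2 makes differences in stage across countries an analytical objective.
- **Staging resources.** Section 1.1 says that "resources available for obtaining correct diagnosis and TNM classification are likely to differ among centres" and gives the lack of PET at many sites as an example.
- **Later information.** Section 4.1.2 records surgery as done or not, with its purpose, and lists no pathological stage. It also collects tests done after diagnosis. Section 6.2 analyses "Changes in the extent of the disease" from baseline to each visit. No section lets a later staging result correct the recorded baseline stage.

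**The concern.** A tissue diagnosis and a finished stage are two different milestones. Entry is tied to the first, and the stage field is tied to the first visit. Where imaging or nodal sampling that belongs to the initial work-up reports after that visit, the recorded stage is provisional, and the protocol as worded keeps it.

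Stage defines the Section 6.2 groups, is a covariate in Section 6.3, and is itself compared between countries under Section 2.1.2. If sites differ in how much staging is done before the first visit, a country could appear to have a different stage mix, or different stage-specific outcomes, because of when stage was written down. There is also a smaller side effect. Extent of disease continues to be recorded, so a late baseline result could show up as a change in extent when the disease has not changed.

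**Working it through.** **1. Who is affected.** Setting Sections 3.3.2.1, 4.1.1 and 6.2 side by side gives four kinds of patient:

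- Staging complete at the first visit: the recorded stage and group are right.
- Initial work-up still open at the first visit: the recorded stage is provisional and the group may be wrong. These patients are the point.
- Disease advances after baseline: the baseline stage was right and so is the group.
- Resected, with a pathological stage that differs from the clinical one: the clinical baseline stage remains valid as such, but the protocol does not say which basis is meant.

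**2. What can be computed.** The protocol gives no up-staging rate and no figure for how often staging is open at first attendance. Its one calculable sample-size figure, a precision of 0.04 with 600 patients, reproduces (1.96 × √(0.25/600) = 0.0400) but has no bearing here. What follows is illustration only.

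**3. Inputs.** From Section 6.4: about 4,000 patients, 80-90% at IIIb/IV. From Section 1.1: one-year survival of 35% in IIIB/IV on first-line chemotherapy, so mortality of 65%. Assumed: a share u of 2%, 5% or 10% of IIIb/IV patients first recorded at a lower stage, and one-year mortality of 20% at lower stage.

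**4. Contamination of the recorded lower-stage group.** With A patients truly IIIb/IV and L truly lower, the misplaced share is c = uA / (uA + L).

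| u | A = 3,200, L = 800 | A = 3,600, L = 400 |
|---|---|---|
| 2% | 64/864 = 7.4% | 72/472 = 15.3% |
| 5% | 160/960 = 16.7% | 180/580 = 31.0% |
| 10% | 320/1,120 = 28.6% | 360/760 = 47.4% |

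At u = 5% the recorded lower-stage mortality becomes 0.20 × 0.833 + 0.65 × 0.167 = 27.5%, or 0.20 × 0.690 + 0.65 × 0.310 = 34.0%, instead of 20%.

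The split matters. Section 1.1 elsewhere puts more than 70% of patients at locally advanced or disseminated disease. At that limit A = 2,800 and L = 1,200, so u = 5% gives 140/1,340 = 10.4% and a mortality of 0.20 × 0.896 + 0.65 × 0.104 = 24.7%.

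**5. Effect on the stage contrast.** The protocol gives no progression rates, so mortality stands in for progression. Let S be the true one-year survival at lower stage. The observed value is S(1 − c) + 0.35c, and the approximate hazard ratio of advanced to lower stage is ln(0.35)/ln(observed).

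- S = 0.80: 4.70 at c = 0; 3.74 at c = 0.10 (observed 0.755); 2.57 at c = 0.30 (observed 0.665).
- S = 0.70: 2.94 at c = 0; 2.02 at c = 0.30.
- S = 0.90: 9.96 at c = 0; 3.41 at c = 0.30.

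Misplacement in this direction shrinks the contrast. By how much depends on c and S, both unknown.

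**6. Effect on the country comparison.** The recorded advanced share is P(1 − u). With P = 80% in both countries, u = 2% in one and 10% in the other, the recorded shares are 78.4% and 72.0%, a difference of 6.4 percentage points where none exists. With P = 90% they are 88.2% and 81.0%, a difference of 7.2 points.

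**The case against.** The strongest reply is that the first-visit limit only separates baseline variables from repeated ones, and that grouping by baseline stage is the sound choice for a Cox model. Regrouping on later findings would condition on events after baseline. That stands, and the remedy respects it.

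It can also be said that staging may usually be known by then. Section 3.1 equates the first visit with diagnosis (for the questionnaires), admits patients already diagnosed or treated elsewhere, and draws data from the medical record. Section 4.3.1 places evaluation visits after a procedure's results are available. This makes the affected share uncertain and possibly small. It does not remove the gap, because none of these passages says which staging counts as baseline. Section 3.1 also allows retrospective inclusion, where staging may already be complete when the record is read, so the rule may be applied unevenly.

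Section 5.1 leaves completion rules to an eCRF manual and Section 6.1 promises an SAP. Either could add detail, but an SAP cannot recover a stage that was never captured. Section 5.1 also appears to bar later changes to entered data, although that sentence may concern only the form.

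A reader might infer more than the documents support:

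- That every analysis is split by stage. Section 6.2 names particular variables, stage is one covariate in Section 6.3, and the FACT-L, EQ-5D and resource analyses are not stated to be stage-split.
- That fixing histology misplaces patients. Histology defines no group.
- That nothing about the disease is updated. Extent is, although it is not used to correct the groups.
- That errors run mostly toward lower stage. The documents do not say so; the illustration assumes it.

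**Conclusion.** The point holds for one set of patients: those whose initial work-up is still open at first attendance. They can be placed in the wrong Section 6.2 group and carry a wrong stage covariate in Section 6.3. Because the protocol itself expects TNM resources to differ among centres, the error may differ by country, which bears directly on Section 2.1.2.

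The size is unknown. The figures above rest on assumed under-staging rates and an assumed lower-stage mortality. They apply the 35% survival of chemotherapy-treated IIIB/IV patients to misplaced patients without evidence of equal prognosis. They also use a IIIb/IV split that is not the protocol's three groups, so 400-800 is not the size of any analysis group.

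It would go too far to conclude that up-staged patients in general sit in the wrong group, or that groups should follow later findings: a patient who truly progresses is correctly grouped by baseline stage. This is a cheap improvement to data collection that has to be made before data are captured. It is not a demonstrated bias in the results.

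**What to change.** In Section 4.1.1, replace the first-visit limit for stage and TNM with: final baseline stage and TNM from all staging tests completed before the first treatment decision, with date and clinical or pathological basis. For untreated patients the cut-off is the documented decision for supportive care or no active treatment. This second anchor is needed because Section 6.4 expects only 75-80% of IIIb/IV patients to be treated. The remaining 20-25% would be between 0.20 × 3,200 = 640 and 0.25 × 3,600 = 900 patients of the 4,000.

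Record pathological TNM for resected patients in a separate field. In Section 6.2, form the three groups from the final pre-treatment stage and state that they are not updated during follow-up. Use pathological stage only descriptively or in a sensitivity analysis, since it exists only for patients who had surgery.

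This is a data definition and asks for no test beyond routine practice. The cost is one or two eCRF fields and a change of wording, using results already in the medical record. The downside is that stage is entered some weeks after inclusion. Patients already treated elsewhere before first attendance need their own rule, which this change does not supply.
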